8.3.5. Pregnancy

- Details of all pregnancies in female participants will be collected after the start of study intervention and until the EOS.
- If a pregnancy is reported, the investigator should inform the sponsor within 24 hours of learning of the pregnancy and should follow the procedures outlined in [Appendix 7](#).
- Abnormal pregnancy outcomes (eg, spontaneous or elective abortion, fetal death, stillbirth, congenital anomalies, ectopic pregnancy) are considered SAEs.

8.3.7. Medication Errors

Medication error refers to any unintended error in the dosing and/or administration of the study intervention as per instructions in the protocol, for example:

- Wrong study intervention
- Wrong dose (including dosing regimen, strength, form, concentration, amount)
- Wrong route of administration
- Wrong participant (ie, not administered to the intended participant)

8.4. Treatment of Overdose

The LD₅₀ for BOTOX in humans is estimated from primate studies to be approximately 3000 U. This makes accidental injection of a lethal dose highly unlikely, but significant AEs may still occur at doses below the LD₅₀ ([Herrero 1967, Scott 1989](#)).

Excessive doses may produce local or distant, generalized, and profound neuromuscular paralysis. Should accidental injection or oral ingestion occur or overdose be suspected, the participant should be medically monitored for up to several weeks for progressive signs or symptoms of systemic muscular weakness that could be local or distant from the site of injection, and which may include ptosis, diplopia, dysphagia, dysarthria, generalized weakness, or respiratory failure.

If the musculature of the oropharynx and esophagus is affected, aspiration may occur, which may lead to development of aspiration pneumonia. If the respiratory muscles become paralyzed or sufficiently weakened, intubation and assisted respiration may be necessary until recovery takes place. Supportive care could involve the need for a tracheostomy and/or prolonged mechanical ventilation, in addition to other general supportive care. Additional information is available in the IB.

A large black rectangular redaction box covers the majority of the page content, starting below the header and ending above the footer. It is positioned on the left side of the page, with a white vertical margin on its right.

9.2. Sample Size Determination

Approximately 165 participants will be enrolled in a 1:1:1 randomization allocation ratio, yielding approximately 55 participants in the BOTOX high dose group, 55 participants in the BOTOX low dose group, and 55 participants in the placebo group. █

the first time in the history of the world, the people of the United States have been called upon to determine whether they will submit to the law of force, or the law of the Constitution. We have said to the world, we will not submit. And this is the question which this election has placed before every American. We have said we will not submit; and we will not submit, unless compelled by the force of an invader, who has declared that he will enslave us if we do not submit.

9.3. Populations for Analyses

The 2 analysis populations are defined below:

- The mITT population includes all randomized participants with ≥ 1 postbaseline assessment for the primary efficacy endpoint. Participants will be summarized according to the randomized study intervention.

BOTOX

- The safety population includes all randomized participants who are administered study intervention. Participants will be summarized according to the study intervention they received.

9.4. Statistical Analyses

The SAP and PRO SAP for psychometric analysis will be developed and finalized before database lock and will describe the participant populations to be included in the analyses, and procedures for accounting for missing, unused, and spurious data. This section summarizes the main features of the planned statistical analyses of the primary and secondary endpoints.

9.4.1. Efficacy Analyses

9.4.1.1. Primary and Secondary Endpoints

The primary and secondary efficacy endpoints will be analyzed for the mITT population ([Table 9-2](#)). All other efficacy endpoints and analyses will be defined in the SAP.

Table 9-2 Primary and Secondary Endpoints

Endpoint	Description	Timing	Methodology
C-APPS Responder (primary endpoint)	Achievement of \geq 1-grade C-APPS improvement at maximum contraction [REDACTED] [REDACTED] at Day 14	Day 14	Responder
P-APPS Responder (secondary endpoint)	Achievement of \geq 1-grade P-APPS improvement at maximum contraction [REDACTED] [REDACTED] at Day 14	Day 14	Responder

9.4.1.2. Multiple Comparisons Procedure

The overall FWER will be controlled at $\alpha = 0.05$ for the set of primary and secondary endpoint comparisons between each of the BOTOX groups versus placebo (4 comparisons). The overall serial gatekeeping MCP will be used to control FWER and is defined in [Table 9-3](#).

Table 9-3 Multiple Comparisons Procedure

MCP Step ^a	Endpoint	MCP Criteria
1	C-APPS responder (BOTOX high dose vs placebo)	Nominal p-value $\leq \alpha$
2	P-APPS responder (BOTOX high dose vs placebo)	Nominal p-value $\leq \alpha$
3	C-APPS responder (BOTOX low dose vs placebo)	Nominal p-value $\leq \alpha$
4	P-APPS responder (BOTOX low dose vs placebo)	Nominal p-value $\leq \alpha$

^a Serial gatekeeping MCP only proceeds to next step if all endpoints are statistically significant after application of MCP criteria in previous and current MCP steps for a BOTOX group.

BOTOX

9.4.1.3. Primary and Secondary Analyses

The proportion of responders will be analyzed using CMH tests [REDACTED]. In addition, 2-sided 95% confidence intervals for the treatment differences in response rates will be provided. Between group comparisons will only be performed for each BOTOX group against the placebo group, and BOTOX high dose group against the BOTOX low dose group.

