## 4.0 INTRODUCTION

This statistical analysis plan (SAP) provides a more technical and detailed elaboration of the statistical analyses of the efficacy and safety data as outlined and/or specified in the protocol of Study 1936-201-008 (Amendment 1 dated 12 August 2019). Specifications of tables, figures, and data listings will be provided in a separate document.

Analyses for patient-reported outcomes (PROs) will be specified in a separate document, and the results will be summarized in a separate report. However, analyses for the Participant Allergan Platysma Prominence Scale (P-APPS) will be described in this document.

Study 1936-201-008 is a Phase 2, multicenter, randomized, double-blind, placebo-controlled, parallel-group, dose-ranging study.
Platysma prominence will be assessed at maximum contraction by the investigator using the C-APPS and by the participant using the P-APPS.
The length of this study will be approximately 4 months for each participant. Signed informed consent from the participant will be obtained at Screening (Day -14 to Day -7) before any study-related procedures. After verification that the participant meets all inclusion and exclusion criteria, and completion of all baseline study procedures, the participant will be randomized in a 1:1:1 ratio to receive BOTOX® high dose, BOTOX low dose or placebo at Visit 2/Day 1.
After
randomization on Day 1, participants will return to the research facility at Days 7, 14, 30, 60, and 90 (Visits 3 to 7, respectively) for protocol-defined efficacy and safety assessments. Study exit protocol-defined assessments will occur at Day 120 (Visit 8) or at early termination.

The schedule of activities is presented in Table 4-1 (footnotes refer to sections within the protocol).

Table 4-1 **Schedule of Activities** 

	Visit 1	Visit 2	Visit 3	Visit 4	Visit 5	Visit 6	Visits 7	Visit 8
Study Procedures	Screening Day -14 to Day -7	Baseline/ Randomization/ Treatment Day 1 a	Day 7	Day 14	Day 30	Day 60	Day 90	Study Exit b Day 120
Visit Windows	-	-	± 3 Days	± 3 Days	± 3 Days	± 7 Days	± 7 Days	± 7 Days
Informed Consent, Privacy Authorization	X							
Inclusion/Exclusion Criteria	X	X						
Demographics	X							
Medical/Surgical History	X							
Weight	X	X	X	X	X	X	X	X
Fitzpatrick Skin Phototype d	X							
Abbreviated Physical Examination e	X							
Vital Signs f	X	X	X	X	X	X	X	X
Urine Pregnancy Test (WOCBP only)g	X	X						X

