#### 11.0 EFFICACY ANALYSES

The efficacy analyses will be based on the mITT population. Observed data will be used for all analyses. Baseline for efficacy is defined as the last non-missing efficacy assessment before study intervention.

The following set of hypotheses will be used to compare the BOTOX groups with placebo for the primary endpoint analysis:

 Null hypothesis: BOTOX and placebo are equally effective in the probability of achieving ≥ 1-grade improvement in the C-APPS score from baseline at Day 14.

 Alternative hypothesis: BOTOX and placebo are not equally effective in the probability of achieving ≥ 1-grade improvement in the C-APPS score
 from baseline at Day 14.

The following set of hypotheses will be used to compare the BOTOX groups with placebo for the secondary endpoint analysis:

- Null hypothesis: BOTOX and placebo are equally effective in the probability of achieving ≥ 1-grade improvement in the P-APPS score from baseline at Day 14.
- Alternative hypothesis: BOTOX and placebo are not equally effective in the probability of achieving ≥ 1-grade improvement in the P-APPS score
   from baseline at Day 14.

For the primary endpoint analysis, the Cochran-Mantel Haenszel (CMH) test will be used to evaluate the equality of responder proportions of C-APPS between study intervention groups.

The BOTOX high dose group will be compared to the placebo group, and the BOTOX low dose group will be compared to the placebo group using a gate-keeping strategy (Dmitrienko 2005). If the comparison of the BOTOX high dose group versus the placebo group yields a p-value at the 0.05 significance level, the BOTOX low dose group will then be compared with the placebo group at the same 0.05 significance level. Otherwise, the BOTOX low dose group will not be considered statistically significantly superior to the placebo group, regardless of its p-value. (see Section 11.3.)

Similarly, for the secondary endpoint analysis, the statistical comparisons will be conducted for the P-APPS.

All statistical tests will be 2-sided hypothesis tests performed at the 0.05 level of significance for main effects. Wald confidence intervals for proportions of responders and difference in the proportion of responders will also be presented. All confidence intervals will be 2-sided 95% confidence intervals.

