#### 17.0 CHANGES TO ANALYSES SPECIFIED IN PROTOCOL

The hypothesis wording has been updated.

In addition, categorical descriptive statistics will be presented for all visits for C-APPS and P-APPS scores,

All PROs except for P-APPS will be reported and summarized in a separate report.

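### Does the SAP drop the protocol's comparison of the high dose with the low dose?

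*Protocol*

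**What the plan says.** Protocol section 9.4.1.3 plans CMH tests of the responder proportions and states that "2-sided 95% confidence intervals for the treatment differences in response rates will be provided". It then gives a closed list of contrasts: each BOTOX group against placebo, and the "BOTOX high dose group against the BOTOX low dose group". Protocol section 9.4.1.2 and Table 9-3 control the familywise error over four comparisons, all of BOTOX against placebo.

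SAP section 11.0 states hypotheses for BOTOX against placebo only, and describes the tested pairs as follows: "The BOTOX high dose group will be compared to the placebo group, and the BOTOX low dose group will be compared to the placebo group". Table 11-1 repeats the protocol's four steps. The same section also uses wider language. The CMH test is to "evaluate the equality of responder proportions of C-APPS between study intervention groups", and "Wald confidence intervals for proportions of responders and difference in the proportion of responders will also be presented". Neither sentence says which pairs of groups it covers.

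SAP section 4.0 describes the document as a "more technical and detailed elaboration of the statistical analyses of the efficacy and safety data as outlined and/or specified in the protocol". SAP section 17.0, on changes from the protocol, opens with "The hypothesis wording has been updated". Its other readable items concern descriptive statistics and the reporting of patient-reported outcomes. The contrast between the doses is not mentioned there.

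**The concern.** The protocol names a contrast between the two active doses, and the more detailed document never repeats it. Readers expect section 17.0 of the SAP to record anything removed, and its readable text records nothing of the kind. Taken at face value, an analysis was planned and then disappeared.

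The trial is titled dose-ranging, so the difference between doses is a natural question. Without a direct estimate, readers would set two comparisons with placebo side by side. Finding one dose significant and the other not says little about how the doses differ, and finding both significant does not settle it either. The fixed testing sequence adds to the unease, because the low dose may never be formally tested. If the contrast were really gone, the report would lack the interval that shows how much, or how little, the data say about dose.

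**Working it through.** **1. Inputs.** 165 randomised 1:1:1, so 165 / 3 = 55 per group (Protocol section 9.2; the SAP gives the same figures). Attrition is about 10%, and 165 × 0.90 = 148.5, which matches the stated 148. Per group, 148 / 3 ≈ 49. The responder rates behind the sample size are not readable, so the rates below are assumptions.

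**2. What the two documents say about the contrast.**

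| Place | High versus low |
|---|---|
| Protocol 9.4.1.3 | Named, with a 95% CI |
| Protocol 9.4.1.2, Table 9-3 | Absent: the family is four placebo comparisons |
| SAP 11.0, hypotheses and gatekeeping text | Absent: these concern comparisons with placebo |
| SAP 11.3, Table 11-1 | Absent: same four steps as Table 9-3 |
| SAP 11.0, CMH and Wald CI sentences | Pairs not specified; the contrast fits |
| SAP 17.0, readable part | No removal recorded |

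Absence from Table 11-1 is not evidence of removal. The protocol's Table 9-3 omits the pair in the same way while section 9.4.1.3 of that protocol plans it, because the contrast lies outside the error-controlled family. The hypotheses in SAP 11.0 are introduced as those for comparing BOTOX with placebo, so they would not be expected to cover it. No readable sentence in the SAP withdraws it.

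**3. Precision of the contrast if reported.** The Wald 95% half-width is 1.96 × √[pH(1−pH)/49 + pL(1−pL)/49].

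| Assumed low / high | Half-width |
|---|---|
| 40% / 50% | 1.96 × √[(0.24+0.25)/49] = 0.196 |
| 50% / 60% | 1.96 × √[(0.25+0.24)/49] = 0.196 |
| 60% / 70% | 1.96 × √[(0.24+0.21)/49] = 0.188 |
| 70% / 80% | 1.96 × √[(0.21+0.16)/49] = 0.170 |
| 80% / 90% | 1.96 × √[(0.16+0.09)/49] = 0.140 |

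For the four rows from 40% to 80%, an observed 10-point advantage would have an interval from about −7 to −10 at the lower end to about +27 to +30 at the upper end. At 49 per group and two-sided 0.05, power for a true 10-point difference is about 17% (50% against 60%) to 28% (80% against 90%). The difference detectable with 80% power is about 18 points for a low-dose rate of 80% and about 28 points for a rate of 40%.

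**4. What a reader could recover in any case.** The SAP presents Wald intervals for the responder proportions. Two independent Wald half-widths combine as √(hH² + hL²). For 70% and 60%: hH = 1.96 × √(0.21/49) = 0.128, hL = 1.96 × √(0.24/49) = 0.137, and √(0.128² + 0.137²) ≈ 0.188, the value in the table. The unadjusted interval therefore follows from the by-group results.

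**The case for a change.** The strongest case for action is that an analysis named in the protocol should not depend on how a programmer reads generic wording. The only pairs the SAP spells out are placebo contrasts, so one analyst could produce the high-minus-low row and another could leave it out. One sentence would settle it at no cost in alpha, because the contrast is outside the four-comparison family. Two placebo comparisons are also a poor substitute for a direct estimate.

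Much of this is fair. The SAP could have been more explicit, and the interval is more informative than a pair of p-values. Two points limit its force. First, the protocol list is explicit and the SAP elaborates it, so leaving the row out would depart from the protocol; it is not an equally valid reading. Second, the readable SAP has gaps: the CMH sentence in section 11.1, a sentence in 11.4 and one in 17.0 break off, and table specifications sit in a separate document. The contrast may be named in text that cannot be read here, so its absence from the SAP cannot be established.

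The point about the fixed sequence does not carry over. Naming high versus low would not alter whether the low dose is formally tested against placebo.

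**Conclusion.** The mismatch is real but small. The protocol names the dose contrast, and the readable SAP neither repeats nor withdraws it. This is missing detail that an analyst holding both documents would fill sensibly, by reporting the Day 14 high-minus-low difference in C-APPS and P-APPS responder proportions with its 95% interval as a nominal estimate. Following the documents as written gives sound results. The stated efficacy objectives compare each dose with placebo, and those four comparisons, the alpha level and the sample size are untouched either way.

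The half-width of about 17 to 20 points measures how imprecise the contrast is with 49 per group. It does not measure harm from the SAP's silence, and added wording would not narrow it. It rests on assumed responder rates 10 points apart between 40% and 80%; rates of 80% and 90% would give about 14 points. Confidence in the textual reading is moderate because of the gaps in the SAP. No change to the plan follows.

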9.4.2. Safety Analyses

The safety analyses will be performed using the safety population and will be fully defined in the SAP. The safety parameters will include AEs and vital signs. For each safety parameter, the last nonmissing safety assessment before the first dose of study intervention will be used as the baseline for all analyses of that safety parameter.

9.4.2.1. Adverse Events

An AE will be considered a TEAE if:

- The AE began after the first dose of study intervention; or
- The AE was present before the first dose of study intervention, but increased in severity or became serious after the first dose of study intervention

An AE will be considered a serious TEAE if it is a TEAE that additionally meets any SAE criteria.

The total number and percentage of participants reporting AEs, TEAEs, treatment-related TEAEs, serious TEAEs, treatment-related serious TEAEs, deaths, and discontinuations due to TEAEs will be summarized for each treatment group.

The number and percentage of participants reporting TEAEs in each study intervention group will be tabulated by system organ class, preferred term, and severity.

The number and percentage of participants reporting serious TEAEs in each study intervention group will be tabulated by system organ class and preferred term.

The number and percentage of participants reporting treatment-related TEAEs in each study intervention group will be tabulated by system organ class and preferred term.

If more than 1 AE is coded to the same PT for the same participant, the participant will be counted only once for that preferred term using the most severe and most related occurrence for the summarizations by severity and by relationship to study intervention.

The number and percentage of participants reporting TEAEs that are included in the possible distant spread of toxin (PDSOT) term list in each study intervention group will be tabulated by preferred term. The PDSOT term list will be provided by the medical safety physician (MSP).

The PDSOT will be reviewed by the MSP on a monthly basis for monitoring severity, frequency, and trending.

CONFIDENTIAL

Protocol 1936-201-008 Amd 1

BOTOX

Listings of all AEs, SAEs, and AEs leading to discontinuation by participant will be presented.

The definitions of an AE and SAE can be found in [Appendix 3](#).

[REDACTED]

9.4.2.3. Vital Signs

Descriptive statistics for vital signs (systolic and diastolic BP, pulse rate, and respiration rate) at baseline and changes from baseline at each assessment will be presented by study intervention.

9.4.3. Other Analyses

All other exploratory efficacy analyses will be described in the SAP. Psychometric analysis will be performed by a CRO and described in a separate PRO SAP.

9.5. Interim Analyses

Interim analyses are not planned for this study.

10. Supporting Documentation and Operational Considerations

10.1. Appendix 1: Regulatory, Ethical, and Study Oversight Considerations

10.1.1. Regulatory and Ethical Considerations

- This study will be conducted in accordance with the protocol and with the following:
 - Consensus ethical principles derived from international guidelines including the Declaration of Helsinki and CIOMS International Ethical Guidelines
 - Applicable ICH/ISO/GCP guidelines
 - Applicable laws and regulations
- The protocol, protocol amendments, ICF, IB, and other relevant documents (eg, advertisements) must be submitted to an IRB/IEC by the investigator and reviewed and approved by the IRB/IEC before the study is initiated.
- Any amendments to the protocol will require IRB/IEC approval before implementation of changes made to the study design, except for changes necessary to eliminate an immediate hazard to study participants.
- The investigator will be responsible for the following:
 - Providing written summaries of the status of the study to the IRB/IEC annually or more frequently in accordance with the requirements, policies, and procedures established by the IRB/IEC
 - Notifying the IRB/IEC of SAEs or other significant safety findings as required by IRB/IEC procedures
 - Providing oversight of the overall conduct of the study at the site and adherence to requirements of applicable local regulations, for example 21 CFR, ICH guidelines, the IRB/IEC, and European regulation 536/2014 for clinical studies (if applicable)

10.1.2. Financial Disclosure

Investigators and subinvestigators will provide the sponsor with sufficient, accurate financial information as requested to allow the sponsor to submit complete and accurate financial certification or disclosure statements to the appropriate regulatory authorities. Investigators are responsible for providing information on financial interests during the study and for 1 year after completion of the study.

10.1.3. Informed Consent Process

- The investigator or his/her representative will explain the nature of the study to the participant and answer all questions regarding the study.
- Participants must be informed that their participation is voluntary. Participants will be required to sign a statement of informed consent that meets the requirements of 21 CFR 50, local regulations, ICH guidelines, HIPAA requirements, where applicable, and the IRB/IEC or study center.
- The medical record must include a statement that written informed consent was obtained before the participant was enrolled in the study and the date the written consent was obtained. The authorized person obtaining the informed consent must also sign the ICF.
- Participants must be re-consented to the most current version of the ICF(s) during their participation in the study.
- A copy of the ICF(s) must be provided to the participant or the participant's legally authorized representative.
- Participants who are rescreened are not required to sign a new ICF if rescreening occurs within 14 days of first signing the ICF.

